### **3.3.4 Removal of subjects from therapy or assessments**

#### **3.3.4.1 Removal of individual subjects**

An individual subject is to be removed from the trial if:

1. The subject withdraws consent, without the need to justify the decision
2. The subject needs to take concomitant drugs that interfere with the investigational product or other trial medication
3. The subject is no longer able to participate for other medical reasons (such as pregnancy, surgery, adverse events, or diseases)
4. The subject shows an elevation of AST and/or ALT  $\geq 3$ -fold ULN combined with an elevation of total bilirubin  $\geq 2$ -fold ULN (measured in the same blood sample) and/or needs to be followed up according to the 'DILI checklist' provided in the ISF.

A subject can also be removed from the trial if eligibility criteria are being violated or if the subject fails to comply with the protocol (for instance, by non-adherence to dietary rules, or non-attendance at study assessments).

If a subject is removed from or withdraws from the trial prior to first administration of trial medication in run-in period, the data of this subject will not be entered in the case report form (CRF) or trial database and will not be reported in the clinical trial report (CTR). If a subject is removed from or withdraws from the trial after first administration of trial medication in run-in period, this will be documented and the reason for discontinuation must be recorded in the CRF. In this case, the data will be included in the CRF/trial database and will be reported in the CTR. At the time of discontinuation a complete end of trial examination will be performed if possible and the information will be recorded in the CRFs. These discontinuations will be discussed in the CTR.

If it is known that a subject becomes pregnant during the trial, administration of the trial medication has to be stopped immediately, and the subject has to be removed from the trial. The subject is to be followed until she has given birth or until the end of pregnancy. The subject's data are to be collected until the end of the trial (last visit of last subject) and reported in the clinical trial report. For reporting of pregnancy and all related events refer to [Section 5.2.2.2](#).

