#### 5.2.2.2 Adverse event collection and reporting

##### **AEs collection**

Upon enrolment into a trial, the subject's baseline condition is assessed (for instance, by documentation of medical history/concomitant diagnoses), and relevant changes from baseline are noted subsequently.

Subjects will be required to report spontaneously any AEs as well as the time of onset, end, and intensity of these events. In addition, each subject will be regularly assessed by the medical staff throughout the clinical trial and whenever the investigator deems necessary. As a minimum, subjects will be questioned for AEs (and concomitant therapies) at the time points indicated in the [Flow Chart](#). Assessment will be made using non-specific questions such as 'How do you feel?'. Specific questions will be asked wherever necessary in order to more precisely describe an AE.

A careful written record of all AEs shall be kept by the investigator in charge of the trial. Records of AEs shall include data on the time of onset, end time, and intensity of the event as well as any treatment or action required for the event and its outcome.

The following must be collected and documented on the appropriate CRF(s) by the investigator:

[figure not shown]
- From signing the informed consent onwards through the residual effect period (REP), until an individual subject's end of trial:
  - All AEs (serious and non-serious) and all AESIs.
  - The only exception to this rule are AEs (serious and non-serious) and AESIs in Phase I trials in healthy volunteers, when subjects discontinue from the trial due to screening failures prior to administration of any trial medication. In

Proprietary confidential information © 2017 Boehringer Ingelheim International GmbH or one or more of its affiliated companies

these cases, the subjects' data must be collected at trial site but will not be entered in the CRF or trial database and will not be reported in the CTR.

- After the individual subject's end of trial:

- The investigator does not need to actively monitor the subject for AEs but should only report relevant SAEs and relevant AESIs of which may become aware of.

The REP for Microgynon® is defined as 10 days after the last administration of Microgynon®.

Therefore, all AEs which occurred through the treatment phase and throughout the REP will be considered as on treatment; please see [Section 7.3.3](#). Events which occurred after the REP will be considered as post treatment events.

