The follow-up period describes the period of time from the last administration of trial medication including the REP until the end of trial examination (last per protocol contact).

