### **6.2.3 End of trial period**

For AE assessment, laboratory tests, recording of ECG and vital signs and physical examination during the end of trial period, see [Sections 5.2.2](#) to [5.2.5](#).

Subjects who discontinue treatment before the end of the planned treatment period should undergo the end of trial visit.

All abnormal values (including laboratory parameters) that are judged clinically relevant by the investigator will be monitored using the appropriate tests until a return to a medically acceptable level is achieved. Adverse events persisting after trial completion must be monitored until they have normalised or have been sufficiently characterised. The end of the trial as a whole is defined by the 'last regular visit completed by last subject' or 'end date of the last open AE' or 'date of the last follow-up test' or 'date of an AE has been decided as sufficiently followed-up', whichever is latest.

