6. GENERAL ANALYSIS DEFINITIONS

6.1 TREATMENT(S)

For basic study information on investigational products, assignments of treatment, and selection of doses, please see CTP, Sections 3 and 4. For details of dosage and formulation see Table 6.1: 1 below.

Table 6.1: 1 Labels for treatments for use in the CTR

Treatment	Substance	Formulation	Unit strength	Dosage	Short label
R1 (Reference 1)	BI 409306	Film coated tablet	25 mg	1 tablet on Day 29	BI
T1 (Test 1)	BI 409306 Microgynon®	Film coated tablet Coated tablet	25 mg 0.03 mg EE / 0.15 mg LNG	1 tablet on Day 18	BI+Microgynon®
R2 (Reference 2)	Microgynon®	Coated tablet	0.03 mg EE / 0.15 mg LNG	1 tablet on Day 17	Microgynon®
T2 (Test 2)	Microgynon® BI 409306	Coated tablet Film coated tablet	0.03 mg EE / 0.15 mg LNG 25 mg	1 tablet on Day 18	BI+Microgynon®

The following separate study phases will be defined for the analyses of AEs:

- Screening (ranging from day of informed consent until first administration of study drug)
- Microgynon® treatment (ranging from the time of first intake of Microgynon® until the time of first administration of BI 409306 or last intake of Microgynon® + Microgynon® REP (10 days), whatever occurs earlier)
- BI 409306 + Microgynon® treatment (ranging from the first administration of BI 409306 + Microgynon® until end of Microgynon® REP (10 days))
- BI 409306 treatment
- Follow up BI 409306 treatment

The residual effect period (REP) for BI 409306, when measurable drug levels or PD effects are still likely to be present, The REP for Microgynon® is considered to be 10 days.

Displays of AEs will be presented separately for the following treatments during on treatment phase:

- BI 409306, tablet, qd (labelled "BI")
- Microgynon®, tablet, qd (labelled "Microgynon")
- BI 409306, tablet, qd + Microgynon®, tablet, qd (labelled "BI + Microgynon")

Two types of AE displays will be provided in the report:

A) Section 15.3 and Appendix 16.1.9.2.8 (for ClinicalTrials.gov) of the CTR displays:

In these displays, the on treatment phase will be analysed (labelled with the name of the study treatment (short label)). Screening and Follow-up BI will not be included in this analysis.

The following total will be provided in addition (Section 15.3 only):

- a total over all on treatment phases involving BI ("Total BI")
- a total over all on treatment phases included in this analysis ("Total on treatment")

B) Section 15.4 and Appendix 16.1.9.2.8 (except for ClinicalTrials.gov) of the CTR displays:

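### For a subject who stops less than 10 days after her last Microgynon® tablet, the end of trial examination closes AE follow-up before the Microgynon® residual effect period has run

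*Protocol*

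**What the plan says.** **Early stop.** Protocol section 3.3.4.1, on a subject who leaves after her first run-in dose: "At the time of discontinuation a complete end of trial examination will be performed if possible and the information will be recorded in the CRFs". Section 6.2.3 adds: "Subjects who discontinue treatment before the end of the planned treatment period should undergo the end of trial visit". It gives no timing relative to the last dose.

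**Collection window.** Protocol section 5.2.2.2 sets the period for collecting all AEs and AESIs: "From signing the informed consent onwards through the residual effect period (REP), until an individual subject's end of trial". It continues: "The REP for Microgynon® is defined as 10 days after the last administration of Microgynon", and "all AEs which occurred through the treatment phase and throughout the REP will be considered as on treatment".

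**Where contact ends.** The same section says that follow-up runs "from the last administration of trial medication including the REP until the end of trial examination (last per protocol contact"). Once the individual's trial has closed, the duty is narrower: "The investigator does not need to actively monitor the subject for AEs but should only report relevant SAEs and relevant AESIs". This covers only events that come to the investigator's notice.

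**Analysis.** SAP section 6.1 ends the Microgynon® phase for AEs at the first BI 409306 dose or "last intake of Microgynon® + Microgynon® REP (10 days), whatever occurs earlier". The combination phase in the same section runs to the end of the Microgynon® REP.

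**The concern.** An examination held on the day a subject stops cannot also close a follow-up period that contains the next 10 days. For a completer the schedule fits, because the examination comes after the REP has ended. For an early stopper neither document schedules a later visit or call. The weekly phone contacts in Flow Chart footnote 9 belong to the run-in only.

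At stake are the on-treatment AE tables. The SAP assigns the 10 days to treatment for every subject. For early stoppers, some or all of those days may have had no contact at which a new non-serious AE would come to light. The tables would then combine fully observed subjects with partly observed ones, and could under-count events after early stopping.

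**Working it through.** **Inputs**
- REP: 10 days after the last Microgynon® tablet (Protocol 5.2.2.2).
- Tablets: run-in to Day -8, none on Days -7 to -1, then Days 1 to 21 (Synopsis; section 3.1). Day 1 follows Day -1 directly, so there is no Day 0.
- End of trial examination for completers: Days 33 to 35 (Flow Chart).
- Examination for early stoppers: at discontinuation (section 3.3.4.1).

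The 10 days are a definition, so there is no plan calculation to reproduce. The check is calendar arithmetic.

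**Formula.** Let L be the day of the last tablet and S the day of the last contact. Then REP end = L + 10, and uncovered days = max(0, L + 10 − S), counted without a Day 0.

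**Completers.** 21 + 10 = Day 31. The examination on Days 33 to 35 leaves a margin of 33 − 31 = 2 to 35 − 31 = 4 days, so the whole REP is covered.

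**Early stoppers, with stop and examination on the same day**

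| Day of stop (S) | Last tablet (L) | REP end | Uncovered days |
|---|---|---|---|
| Any dosing day, e.g. Day 10 | 10 | 20 | 10 |
| Day -8 | -8 | 3 | 10 |
| Day -7 | -8 | 3 | 9 |
| Day -1 | -8 | 3 | 3 |
| Day 21 | 21 | 31 | 10 |
| Day 22 | 21 | 31 | 9 |
| Day 25 | 21 | 31 | 6 |
| Day 28 | 21 | 31 | 3 |
| Day 29 | 21 | 31 | 2 |
| Day 30 | 21 | 31 | 1 |
| Day 31 or later | 21 | 31 | 0 |

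An examination held d days after the stop reduces each gap by d days, down to 0. The full 10-day gap is possible on any of the 21 + 21 = 42 to 42 + 21 = 63 dosing days.

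**Link to the analysis.** A subject who stops before Day 18 never receives BI 409306, so her Microgynon® phase runs to last intake + 10 days. A subject who stops from Day 18 but before the Day 29 dose is in the combination phase, which also runs to the end of the Microgynon® REP. In both cases the SAP counts the uncovered days as on treatment.

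**Sensitivity of the tables.** SAP section 7.8.1 counts subjects with AEs and has a separate table of non-serious AEs above 5% incidence per preferred term. With the 16 planned subjects as denominator, one subject is 1/16 = 6.25%. One missed non-serious AE could therefore decide whether a term appears there.

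**The case against.** The strongest reply is that the duty already exists. Section 5.2.2.2 asks for collection through the REP without excepting early stoppers. Section 3.3.4.1 orders a set of procedures and does not say that they end AE collection. Section 6.2.3 leaves the timing of the visit open. This shows that the plan meant the REP to be covered, but it does not remove the conflict. Section 5.2.2.2 makes the examination the last contact, section 3.3.4.1 fixes when it happens, and nothing later is scheduled.

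Several other points stand and limit the concern:
- **Which events.** A reader might infer that thromboembolism or liver injury in an early stopper would go unrecorded. The documents do not support that. Protocol section 1.2.2 classes venous and arterial thromboembolism as serious, and section 5.2.2.1 makes hepatic injury an AESI. Relevant SAEs and AESIs stay reportable after the end of trial, although only if they become known. AEs already open are followed (sections 5.2.2.2 and 6.2.3).
- **How much.** A reader might also infer that every dropout loses the whole REP. That needs a stop and an examination on the same dosing day. Run-in tablets are taken at home, so a same-day examination may be unlikely there.
- **How many.** No dropout rate is given. A subject who withdraws consent cannot be obliged to take a later call.
- **Analysis.** Safety is descriptive only, and time on Microgynon® already varies by design (21 to 42 run-in days).

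**Conclusion.** The conflict is real and its reach is limited. It affects a subject who discontinues less than 10 days after her last Microgynon® tablet and is examined before those 10 days are over. She loses active ascertainment, mainly of new non-serious AEs, for at most 10 days, with the gradient shown in the working. The consequence is possible under-counting in descriptive on-treatment AE tables for early stoppers. Completers, anyone stopping from Day 31, and the primary and secondary PK endpoints are unaffected.

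This rests on the examination falling on the day of the stop and on no later contact being scheduled outside the visible text. The number of subjects affected cannot be estimated from the documents. The REP of BI 409306 is not visible in the public text, so its coverage was not assessed.

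**What to change.** Keep the examination at discontinuation. Reconcile Protocol sections 3.3.4.1, 5.2.2.2 and 6.2.3 by stating that AE collection for an early stopper continues until the latest REP end among all trial drugs she has taken. Where the examination falls before that day and the subject agrees to be contacted, add one phone contact then, covering AEs and concomitant therapy. Adjust the definition of the final contact in section 5.2.2.2 to match.

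The rule should not refer only to the last drug taken. After the Day 29 dose, that drug is BI 409306. If its REP were under 2 days (an assumption, since the figure is not visible), collection could close before the Microgynon® REP ends on Day 31.

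The cost is a few sentences in the protocol and one call per early stopper, with no change for completers. Subjects who withdraw consent may remain unreachable. The change belongs in the protocol, because AEs that were never collected cannot be recovered at analysis.

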#### **3.3.4.2 Discontinuation of the trial by the sponsor**

Boehringer Ingelheim reserves the right to discontinue the trial overall or at a particular trial site at any time for any of the following reasons:

1. New toxicological findings or serious adverse events invalidate the earlier positive benefit-risk-assessment. More specifically, the trial will be terminated if more than 50%

Proprietary confidential information © 2017 Boehringer Ingelheim International GmbH or one or more of its affiliated companies

of the subjects show drug-related and clinically relevant adverse events of moderate or severe intensity, or if at least one drug-related serious adverse event is reported that is considered to be unacceptable.

2. The expected enrolment goals overall are not met
3. Violation of GCP, or the CTP, or the contract with BI by a trial site or investigator, disturbing the appropriate conduct of the trial
4. The sponsor decides to discontinue the further development of the investigational product.

The investigator / the trial site will be reimbursed for reasonable expenses incurred in case of trial termination (except in case of the third reason).

### **3.3.5 Replacement of subjects**

In case some subjects do not complete the trial, the trial clinical monitor together with the trial pharmacokineticist and the trial statistician are to decide if and how many subjects will be replaced. A replacement subject will be assigned a unique study subject number.

## **4. TREATMENTS**

### **4.1 TREATMENTS TO BE ADMINISTERED**

#### **4.1.1 Identity of BI investigational product and comparator product.**

##### **Trial Product 1**

Substance: BI 409306

Pharmaceutical formulation: film-coated tablet

Source: BI Pharma GmbH & Co. KG, Germany

Unit strength: 25 mg

Posology: 1-0-0

Route of administration: p.o.

Duration of use: Days 18 and 29

##### **Trial Product 2**

Name: Microgynon® 30

Substance: ethinylestradiol (EE) and levonorgestrel (LNG)

Pharmaceutical formulation: coated tablet (sugar-coated)

Source: Bayer plc, Bayer House

Unit strength: 0.03 mg EE and 0.15 mg LNG

Posology: 1-0-0

Route of administration: p.o.

Duration of use: Maximum 42 days in run-in period, 21 days in treatment period

#### **4.1.2 Method of assigning subjects to treatment groups**

This is an open-label, two-period, fixed-sequence trial.

The allocation of subjects to study subject numbers will be performed after screening. Once a subject number has been assigned, it cannot be reassigned to any other subject.

#### **4.1.3 Selection of doses in the trial**

The ethinylestradiol/levonorgestrel (Microgynon®) doses of 0.03 / 0.15 mg QD are standard clinical doses and were selected to achieve a the relevant plasma exposure for evaluation of a possible drug-drug interaction (see [section 1.2](#)).

#### **4.1.4 Drug assignment and administration of doses for each subject**

All subjects will receive the two treatments in a fixed sequence order. The treatments to be evaluated are outlined in Table 4.1.4: 1 below.

**Table 4.1.4: 1 Dosage and treatment schedule**

Treatment	Substance	Formulation	Unit strength	Dosage
R1 (Reference 1)	BI 409306	Film coated tablet	25 mg	1 tablet on Day 29
T1 (Test 1)	BI 409306	Film coated tablet	25 mg	1 tablet on Day 18
	Microgynon®	Coated tablet	0.03 mg EE / 0.15 mg LNG	1 tablet on Day 18
R2 (Reference 2)	Microgynon®	Coated tablet	0.03 mg EE / 0.15 mg LNG	1 tablet on Day 17
T2 (Test 2)	Microgynon®	Coated tablet	0.03 mg EE / 0.15 mg LNG	1 tablet on Day 18
	BI 409306	Film coated tablet	25 mg	1 tablet on Day 18

#### **Run-in period:**

The Microgynon® tablets for the run-in period (duration depends on the actual menstrual cycle of the subject) will be dispensed to the eligible subjects. The administration during the run-in period is done by the subjects and documented in a diary. The subjects are advised to

Proprietary confidential information © 2017 Boehringer Ingelheim International GmbH or one or more of its affiliated companies

take the Microgynon® tablets with a cup of water at the same time in the morning. No Microgynon® tablets are to be taken in the last 7 days of the run-in period.

**Treatment period:**

The medication will be administered as an oral dose together with about 240 mL of water to a subject in the standing position under supervision of the investigating physician or an authorised designee. The so-called four-eye principle (two-person rule) should be applied for administration of trial medication and – if applicable – its preparation (e.g. reconstitution), if correct dosage cannot be ensured otherwise. Administration in the morning of Days 17, 18 and 29 will be performed following an overnight fast starting no later than 10 h before scheduled dosing. For medication at all other time points no fasting is required.

Subjects will be kept under close medical surveillance for at least 12 h post dose on Days 17, 18 and 29.

During the first 2 h after drug administration on these days, they are not allowed to lie down (i.e. no declination of the upper body of more than 45 degrees from upright posture, except for trial activities). For restrictions with regard to diet see [Section 4.2.2.2](#).

**4.1.5 Blinding and procedures for unblinding**

No blinding was performed because the treatments are distinguishable from each other. This Phase I trial will be handled in an open fashion throughout (that is, during the conduct, including data cleaning and preparation of the analysis). This is considered acceptable because the potential for bias seems to be low and does not outweigh practical considerations.

Emergency envelopes will not be provided, since all subjects receive the same dose of different formulations in an open label design.

**4.1.6 Packaging, labelling, and re-supply**

Drug supplies will be provided by the Department of Pharmaceutical Development of Boehringer Ingelheim Pharma GmbH & Co. KG, Biberach, Germany.

The clinical trial supply consists of containers holding the trial medication which are labelled with trial identification. The clinical trial supply containers for BI 409306 will be labelled with:

- BI trial number
- Batch number
- Name of product and strengths or identification code
- Pharmaceutical dosage form, quantity of dosage units
- Route and mode of administration
- Term 'For Clinical Trial Use' (domestic language)
- Sponsor name and address
- Storage conditions
- Use-by date

The blisters are labelled with reduced requirements.

The telephone number of the sponsor and name, address and telephone number of the trial site are given in the subject information form. Examples of the labels will be available in the ISF.

No re-supply is planned.

#### **4.1.7 Storage conditions**

Drug supplies will be kept in their original packaging and in a secure limited access storage area according to the recommended (labelled) storage conditions. Where necessary, a temperature log must be maintained to make certain that the drug supplies are stored at the correct temperature. If the storage conditions are found to be outside the specified range, the local clinical monitor (as provided in the list of contacts) is to be immediately contacted.

#### **4.1.8 Drug accountability**

The investigator / pharmacist / investigational drug storage manager will receive the investigational drugs delivered by the sponsor when the following requirements are fulfilled:

- Approval of the study protocol by the IRB / ethics committee
- Availability of a signed and dated clinical trial contract between the sponsor and the Head of Trial Centre
- Approval/notification of the regulatory authority, e.g. competent authority
- Availability of the curriculum vitae of the principal investigator
- Availability of a signed and dated clinical trial protocol or immediately imminent signing of the clinical trial protocol

Only authorised personnel as documented in the form 'Trial Staff List' may dispense medication to trial subjects. The trial medication must be administered in the manner specified in the CTP. All unused medication must be returned to the sponsor. Receipt, usage and return must be documented on the respective forms in ISF. Account must be given for any discrepancies.

The investigator / pharmacist / investigational drug storage manager must maintain records of the product's delivery to the trial site, the inventory at the site, the use by each subject, and the returned to the sponsor of unused products.

These records will include dates, quantities, batch / serial numbers and expiry ('use-by') dates. The investigator / pharmacist / investigational drug storage manager will maintain records that document adequately that the subjects were provided the doses specified by the CTP, and that reconcile all investigational products received from the sponsor. At the time of return to the sponsor, the investigator / pharmacist / investigational drug storage manager must verify that all unused or partially used drug supplies have been returned by the clinical trial subject and that no remaining supplies are in the investigator's possession.

